4.1.5 Blinding and procedures for unblinding

The trial has a double-blind design. The randomization schemes and medication kit lists (i.e. the treatment information) will be handled according to the sponsor's Standard Operating Procedures (SOPs).

Refer to section [4.1.5.2](#) for rules of breaking the code for an individual or for all patients in emergency situations.

4.1.5.2 Unblinding and breaking the code

Emergency unblinding will be available to the investigator via IRT. It must be used only in an emergency situation when the identity of the trial drug must be known to the investigator in order to provide appropriate medical treatment or otherwise assure safety of trial participants. The reason for unblinding must be documented in the source documents and/or appropriate CRF page. If the patient is unblinded by the investigator, patient will have to be discontinued from the trial. Discontinued patients will complete the EoT and follow-up visits.

Due to the requirements to report Suspected Unexpected Serious Adverse Reactions (SUSARs), it may be necessary for a representative from BI's Pharmacovigilance group to access the randomization code for individual patients during trial conduct. The access to the

Clinical Trial Protocol

Proprietary confidential information © 2025 Boehringer Ingelheim International GmbH or one or more of its affiliated companies

code will only be given to authorized Pharmacovigilance representatives for processing in the PV database system and not be shared further.

4.1.6 Packaging, labelling, and re-supply

The investigational medicinal products will be provided by BI or a designated contract research organization (CRO). They will be packaged and labelled in accordance with the principles of Good Manufacturing Practice. Re-supply (if necessary) will be managed via the IRT system. For details of packaging and the description of the label, refer to the ISF.

4.1.7 Storage conditions

Drug supplies will be kept in their original packaging according to the recommended storage conditions on the medication label. Patients will be instructed to store the medication in a secure area. Site staff will train the patients on storage conditions. Patients will not maintain a temperature log.

If shipment of trial medication to the site becomes necessary (section [4.1.4](#)), sites should store the medication in a secure limited access storage area according to the recommended storage conditions on the medication label, and maintain a temperature log until the medication is dispensed to the patient. If the storage conditions are found outside the specified range, procedure described in the ISF has to be followed and a Clinical Research Associate (CRA) should be contacted immediately.

4.1.8 Drug accountability

The patient will receive the investigational drug delivered by the sponsor when the following requirements are fulfilled at the study site:

- Approval of the clinical trial protocol by the Institutional Review Board (IRB) / ethics committee,
- Availability of a signed and dated clinical trial contract between the sponsor or delegate and the investigational site,
- Approval/notification of the regulatory authority, e.g. competent authority,
- Availability of the curriculum vitae of the Principal Investigator,
- Availability of a signed and dated clinical trial protocol,
- Availability of the proof of a medical license for the Principal Investigator,
- Availability of Food and Drug Administration (FDA) Form 1572 (if applicable),
- Study site has obtained a signed informed consent from the patient.

Investigational drugs are not allowed to be used outside the context of this protocol. They must not be forwarded to other investigators or clinics. Patients should be instructed to return all unused investigational drug.

The investigator or designee must maintain records of the product's delivery to the patient, the use by each patient, and the return to the sponsor or warehouse / drug distribution center

Clinical Trial Protocol

Proprietary confidential information © 2025 Boehringer Ingelheim International GmbH or one or more of its affiliated companies

or alternative disposal of unused products. If applicable, the sponsor or warehouse / drug distribution center will maintain records of the disposal. These records will include dates, quantities, batch / serial numbers, expiry ('use-by') dates, and the unique code numbers assigned to the investigational medicinal product and trial patients. The investigator or designee will maintain records that document adequately that the patients were provided the doses specified by the Clinical Trial Protocol and reconcile all investigational medicinal products the patient received from the sponsor. At the time of return to the sponsor and/or appointed CRO, the investigator or designee must verify that all unused or partially used drug supplies have been returned by the patient and that no remaining supplies are in the investigator's possession.

4.2 OTHER TREATMENTS, EMERGENCY PROCEDURES, RESTRICTIONS

4.2.1 Other treatments and emergency procedures

There are no special emergency procedures to be followed in this trial.

4.2.2 Restrictions

4.2.2.1 Restrictions regarding concomitant treatment

Medication or class of medications	Restriction needs and time
Strong inhibitors and strong inducers of CYP3A4/5; immunosuppressive agents, drugs with UGT1A4 activity, drug which are known P-gp substrates of narrow therapeutic window, and OCT2, MATE1, or MATE2-K substrates.	Not allowed 1 week or 5 half-lives (whichever is longer) prior to randomization through 5 days after EOT
Investigational device or drug	Not allowed 30 days or 5 half-lives (whichever is longer) prior to randomization through 5 days after EOT
Agents known to prolong the QT interval	Not allowed 1 week or 5 half-lives (whichever is longer) prior to randomization through 5 days after EOT
Systemic corticosteroids	Dose must be stable for at least 4 weeks prior to screening visit. Dose should not change during the screening and treatment period unless the investigator feels a dose change is necessary to ensure the patient's safety.

Clinical Trial Protocol

Proprietary confidential information © 2025 Boehringer Ingelheim International GmbH or one or more of its affiliated companies

Additional information, including a list of drugs that should be avoided, is provided in the ISF for the following classes of medications: immunosuppressive agents, strong inhibitors/inducers of CYP3A4/5, UGT1A4, drugs which are known P-gp substrates of narrow therapeutic window, and OCT2, MATE1, or MATE2-K substrates as well as agents known to prolong the QT interval.

Medications listed under the exclusion criteria (section [3.3.3](#)), are not allowed during the trial. When possible, use of restricted medications and impact on treatment discontinuation should be discussed with the sponsor. There are no restrictions for trial participant to receive vaccination for COVID-19 during or after the study period.

4.2.2.2 Restrictions on diet and lifestyle

Patients should avoid high protein, high salt diet. Avoidance of dietary protein load and strenuous exercise is especially important within 24 hours prior to the start and until the completion of the 24-hour urine collections.

4.2.2.3 Contraception requirements

Female Patients

WOCBP (for definition refer section [3.3.2](#)) and their male sexual partner must use two medically approved methods of birth control during the treatment period and for a period of at least 5 days after last trial drug intake. Male partner of a WOCBP trial participant who is able to father a child must use a condom.

WOCBP (trial participant) must use a highly effective method of birth control per ICH M3 (R2) that results in a low failure rate of less than 1% per year when used consistently and correctly. Birth control methods with low user dependency, as indicated with an asterisk (*) below are preferable.

- Combined (estrogen and progestogen containing) hormonal birth control that prevents ovulation (oral, intravaginal, transdermal)
- Progestogen-only hormonal birth control that prevents ovulation (oral, injectable, implantable*)
- Intrauterine device (IUD)* or intrauterine hormone-releasing system (IUS)*
- Bilateral tubal occlusion*

Acceptable methods of birth control will include abstinence from male-female sex or having a vasectomized partner, provided that partner is the sole sexual partner of the trial participant who is a WOCBP, and that the vasectomized partner has received medical assessment of the surgical success.

Abstinence from male-female sex is defined as being in line with the preferred and usual lifestyle of the patient. Periodic abstinence e.g. calendar, ovulation, symptothermal, post-ovulation methods; declaration of abstinence for the duration of exposure to study drug; and withdrawal are not acceptable.

Clinical Trial Protocol

Proprietary confidential information © 2025 Boehringer Ingelheim International GmbH or one or more of its affiliated companies

Since BI 764198 is not expected to lead to a clinically relevant reduction in the exposure of oral contraceptives due to an increased metabolism via enzyme induction (section [1.2](#)), oral contraceptives are allowed in this trial.

4.3 TREATMENT COMPLIANCE

Patients are requested to bring all remaining trial medication including empty bottles with them when attending visits. Based on capsule counts, treatment compliance will be calculated as shown in the formula below.

$$\text{Treatment compliance (\%)} = \frac{\text{Number of capsules actually taken} \times 100}{\text{Number of capsules should have been taken as directed by the investigator}}$$

Compliance will be verified by the CRA authorized by the sponsor or delegate. The target for medication compliance should be 100%. If patient is non-compliant, site staff will explain to the patient the importance of treatment compliance. Randomized patients will not be discontinued from the trial for poor medication compliance without prior discussion with the Clinical Trial Manager (CT Manager) appointed by the sponsor.

For patients participating in the trial remotely via the DCT model, compliance will be calculated by the MRN, and all unused trial medication and empty bottles will be collected by the MRN and returned to the study site or an alternative location for disposal. Shipment schedule and guidelines will be described in the DCT operational manual. The investigator or designee must verify that all unused trial medication has been returned by the patient and that no remaining supplies are at the patient's home.

Clinical Trial Protocol

Proprietary confidential information © 2025 Boehringer Ingelheim International GmbH or one or more of its affiliated companies

5. ASSESSMENTS

5.1 ASSESSMENT OF EFFICACY

5.1.1 Measures of proteinuria

The primary endpoint is patients achieving at least 25% reduction in UPCR from 24-hour urine relative to baseline after 12 weeks of treatment. The baseline UPCR will be from the average of two 24-hour urine samples collected before visit 2.

Secondary and [REDACTED] are listed in sections [2.1.3](#) and [REDACTED], respectively, and they will be assessed as follows:

- Change in UPCR relative to visit 3 at week 12: the samples will be from the 24-hour urine samples collected at visits 3 and 12.
- Change in UPCR relative to baseline at week 13: the samples will be the 24-hour urine samples collected at baseline and week 13.
- Change in 24-hour urinary protein excretion relative to baseline at week 12.

For additional information on urine sample collections and the time points, see section [6.1](#) and [Flow Chart A](#).

5.2 ASSESSMENT OF SAFETY

5.2.1 Physical examination

A complete physical examination will be performed at the time points specified in the [Flow Chart A](#). It includes at a minimum general appearance, neck, lungs, cardiovascular system, abdomen, extremities, and skin. Measurement of height and body weight will be performed at the time points specified in the Flow Chart A. The results must be included in the source documents available at the site.

For patients participating in the trial remotely via the DCT model, a physical examination per protocol will be performed at the patient's home at the time points specified in the study protocol. The investigator or a designee (as indicated in the site trial staff list) will supervise

Clinical Trial Protocol

Proprietary confidential information © 2025 Boehringer Ingelheim International GmbH or one or more of its affiliated companies

the physical examination remotely. A MRN will facilitate the physical examination in the patient's home.

For patients participating in the trial remotely, if during the physical examination (PE) or at any time during the trial it is deemed that the patient requires in-person follow-up, the patient will be advised to visit the study site or their healthcare provider or a local facility for consultation. When applicable, the study site staff will contact the local healthcare facility to obtain the medical records.

5.2.2 Vital signs

Vital signs will be evaluated at the time points specified in the [Flow Chart A](#), prior to blood sampling. This includes systolic and diastolic blood pressure and pulse rate (electronically or by palpation count for 1 minute) in a seated position after 5 minutes of rest. Assessment for uncontrolled hypertension is completed at Visit 1 only. Three blood pressure measurements will be taken approximately 2 minutes apart after the patient has rested quietly and is in a seated position for at least 5 minutes. The average of the last two measurements for the triplicate systolic blood pressure measurements should be < 160 mmHg for assessment of exclusion criteria 5 at the screening visit. For subsequent visits, triplicate measurements are needed only if the first reading is >160mmHg, the average of the last two measurements are taken as the final reading. The results must be included in the source documents available at the site.

5.2.3 Safety laboratory parameters

Safety laboratory parameters to be assessed are listed in Table [5.2.3: 1](#). Sampling time points are provided in the Flow Chart A.

All analyses will be performed by a central laboratory, and the respective reference ranges will be provided in the laboratory manual. Instructions regarding sample collection, sample handling, processing, and shipping are provided in the laboratory manual.

If central lab services or the lab kits provided by the central lab are not available at the study site, safety labs may be done at a local lab. The results of the lab tests should be entered in the eCRF. Please note the local labs should be used only if it becomes necessary, and the CT Manager should be informed.

For patients participating in the trial remotely via the DCT model, laboratory kits will be made available at the patient's home for the respective visits. The MRN will collect, process, and ship lab samples to the central laboratory or the study site (when applicable). Additional information will be provided in the DCT operations manual.

Patients do not have to be fasted for the blood sampling for the safety laboratory.

Clinical Trial Protocol

Proprietary confidential information © 2025 Boehringer Ingelheim International GmbH or one or more of its affiliated companies

The central laboratory will send laboratory reports to the investigator. It is the responsibility of the investigator to evaluate the reports. Clinically relevant abnormal findings as judged by the investigator will be reported as AEs (refer to section [5.2.6](#)).

In case the criteria for hepatic injury are fulfilled, a number of additional measures will be performed (section [5.2.6.1](#) and the DILI Checklist provided in the electronic data capture (EDC) system. The amount of blood taken from the patient concerned will be increased due to this additional sampling for DILI assessments. The central laboratory will transfer the data to the sponsor periodically.

For assessment of eGFR exclusion criterion (section [3.3.3](#)), the CKD-EPI formula based on serum creatinine and serum cystatin C will be used. The serum cystatin C-based CKD-EPI formula will be used for the calculation of eGFR in the evaluation of efficacy. [REDACTED]

[REDACTED].

Clinical Trial Protocol

Proprietary confidential information © 2025 Boehringer Ingelheim International GmbH or one or more of its affiliated companies

Table 5.2.3: 1 Safety laboratory tests

Functional lab group	Test name
Haematology	Haematocrit Haemoglobin Red blood cells (RBC) White blood cells (WBC) Platelet count MCV MCH MCHC RDW
Automatic WBC differential (relative and absolute)	Neutrophils total Lymphocytes total Eosinophils Basophils Monocytes Lymphocytes
Manual differential WBC (if automatic differential WBC is abnormal)	Polymorphonuclear neutrophils (segs), band neutrophils (stabs), eosinophils, basophils, monocytes, lymphocytes
Coagulation	Activated partial thromboplastin time (aPTT) Prothrombin Time (PT) International Normalised Ratio (INR)
Enzymes	Aspartate aminotransferase (AST) Alanine aminotransferase (ALT) Alkaline phosphatase (ALP) Gamma-glutamyl transferase (GGT) Creatine Kinase (CK) Creatine kinase – MB fraction (CK-MB ¹) Lactate dehydrogenase Lipase Amylase Troponin I ¹
Substrates	Glucose HbA1c (at screening and EoT) Creatinine (enzymatic method) ² Cystatin C eGFR - CKD-EPI formula based on serum creatinine and cystatin C ³ eGFR - CKD-EPI based on serum creatinine eGFR – CKD-EPI based on serum cystatin C ⁴ Urea Uric Acid

Clinical Trial Protocol

Proprietary confidential information © 2025 Boehringer Ingelheim International GmbH or one or more of its affiliated companies

Table 5.2.3: 1

Safety laboratory tests (cont.)

Functional lab group	Test name
Substrates (cont.)	Total bilirubin Direct bilirubin Total protein Triglycerides Albumin Globulin Albumin / Globulin ratio C-Reactive Protein (CRP) Total cholesterol
Infectious serology ⁵	Hepatitis B surface antigen Hepatitis C antibodies HIV-1/2 combination
Electrolytes	Calcium Sodium Potassium Magnesium Chloride Phosphate Bicarbonate (calculated) anion gap
Urinalysis	Urine nitrite Urine protein Urine glucose Urine ketone Urine bilirubin Urine Blood Urine leukocyte esterase Urine pH Specific gravity Urine drug screen (screening visit only) Cannabis Cocaine Benzodiazepine Amphetamines Barbiturates Methadone Opiates
Urine sediment (microscopic examination if erythrocytes, leukocytes, nitrate or protein are abnormal in urine)	Only positive findings will be reported (e.g. presence of sediment bacteria, casts in sediment, squamous epithelial cells, erythrocytes, leukocytes).
Serum Pregnancy test (only for female participants of childbearing potential) at Visit 1, and if urine pregnancy test is positive at other visits.	Human Serum Chorionic Gonadotropin
Urine pregnancy test	Human Serum Chorionic Gonadotropin

Clinical Trial Protocol

Proprietary confidential information © 2025 Boehringer Ingelheim International GmbH or one or more of its affiliated companies

1. If initial CK is elevated, re-test CK with CK-MB and troponin I.
2. Reported to the investigator only up to visit 2.
3. eGFR based on serum creatinine and cystatin C will be reported to the investigator only up to visit 2.
4. eGFR based on serum cystatin C will be reported to the investigator from visit 2 onwards.
5. Only at screening visit.

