An electrocardiogram (ECG) analysis based on three Phase I trials in healthy volunteers (████████), (c█████0), and (████████) indicated that BI 764198 may cause QT prolongation in a dose-dependent manner for doses ≥ 80 mg BI 764198 once daily. After single and multiple doses of BI 764198, a reversible, dose-dependent increase of serum creatinine was observed in Phase I trials. It is believed that BI 764198 may increase serum creatinine by decreasing renal tubular secretion of creatinine via inhibition of renal transporters (e.g. MATE1) without an impact on kidney function as measured by unchanged cystatin C levels. Cystatin C (in addition to serum creatinine measurements) will be used to assess changes in renal function in patients treated with BI 764198.

Treatment in a proof-of-concept clinical trial 1434-0009 (████████) to reduce the risk/severity of acute respiratory distress syndrome in patients hospitalized for coronavirus disease 2019 (COVID-19) and requiring non-invasive oxygen therapy was terminated early, based on an independent data monitoring committee (DMC) recommendations, due to a clear lack of benefit in this critically ill patient population and a numerical imbalance of fatal events between the active and placebo treatment groups. Fatality rate was still within expected range for hospitalised COVID-19 patients on oxygen ([R20-3802](#)). Based on the totality of the data review from the study, BI has not identified to date any new safety risks for BI 764198. No adverse effects were noted to date which would impact the conduct of ongoing Phase 1 trials in healthy volunteers or the planning of Phase 2 proof-of-concept trials in chronic kidney disease (CKD).

Through favourable effects on glomerulosclerosis, delaying podocyte injury, and improving vascular function, a TRPC6 inhibitor may have the potential to slow disease progression when used on-top-of optimal therapy including ACEi/ARB. Such a therapy could be considered a notable advance in patient health and well-being by slowing progression to ESKD, improving clinical outcomes, reducing disease burden, and improving quality of life in proteinuric glomerular diseases such as FSGS.

For a more detailed description of the profile, refer to the current version of the IB (████████).

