3.3.4.1 Discontinuation of trial treatment

An individual patient will discontinue trial treatment if:

- The patient wants to discontinue trial treatment. The patient will be asked to explain the reasons but has the right to refuse to answer.
- The patient has repeatedly shown to be non-compliant with important trial procedures and, in the opinion of both, the investigator and sponsor representative, the safety of the patient cannot be guaranteed as he/she is not willing or able to adhere to the trial requirements in the future.
- The patient needs to take concomitant medication which may increase their risk of adverse effects or interfere with the investigational medicinal product (section [4.2.2](#)). In cases where treatment is expected to be temporary (short course), the case should be discussed with the sponsor and a decision will be made on potentially restarting trial medication.
- The patient can no longer receive trial treatment for medical reasons (such as surgery, serious or severe drug induced liver injury attributable to the trial drug (section [5.2.6.1.4](#)), other AEs, other diseases, or pregnancy).
- The patient experiences confirmed QT prolongation of QTcF intervals greater than 500 ms or an increase of >60 ms compared to baseline (defined as visit 2, pre-dose measurement).
- The patient experiences clinically relevant conduction disorders (e.g. AV block \geq 2nd degree, bundle branch block).

Clinical Trial Protocol

Proprietary confidential information © 2025 Boehringer Ingelheim International GmbH or one or more of its affiliated companies

- The patient is diagnosed with cataract (graded by LOCS III higher than NC1/NO1, C0, P0) during study treatment.
- eGFR below 25 mL/min/1.73 m² (CKD-EPI formula based on serum cystatin C) and not improved by resolution of transient events (e.g. dehydration).
Patient experiences acute kidney injury as per clinical judgement by the investigator and/or according to the modified Kidney Disease: Improving Global Outcomes (KDIGO) definition ([R17-2439](#)) and adapted for cystatin C as opposed to serum creatinine ([R14-1203](#), [R15-5270](#)).
 - Increase in cystatin C to \geq 1.5 times the baseline value, which is known or presumed to have occurred within the prior 7 days.

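### The creatinine-only eGFR row in Table 5.2.3: 1 has no visible reporting limit, so it can give investigators the creatinine information that footnotes 2 and 3 withhold after visit 2

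*Protocol*

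**What the plan says.** Protocol Section 1.2 describes the drug effect: "After single and multiple doses of BI 764198, a reversible, dose-dependent increase of serum creatinine was observed in Phase I trials". It attributes this to reduced tubular secretion, "without an impact on kidney function as measured by unchanged cystatin C levels". Section 4.1.5 states: "The trial has a double-blind design".

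Table 5.2.3: 1 lists serum creatinine, cystatin C and three versions of eGFR. Reporting to the investigator is set by footnote:

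- **Serum creatinine (footnote 2):** "Reported to the investigator only up to visit 2".
- **Combined eGFR (footnote 3):** "eGFR based on serum creatinine and cystatin C will be reported to the investigator only up to visit 2".
- **Cystatin C eGFR (footnote 4):** reported from visit 2 onwards.
- **Creatinine-only eGFR:** the row reads "eGFR - CKD-EPI based on serum creatinine" and has no footnote.

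Section 5.2.3 gives the default: central laboratory reports go to the investigator, who must evaluate them. It also allows a fallback when central services or kits are unavailable: "safety labs may be done at a local lab. The results of the lab tests should be entered in the eCRF". That route is for necessity only, and the trial manager must be told. No exception for creatinine is visible.

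In Section 3.3.4.1, the eGFR threshold and the numeric acute kidney injury criterion both use cystatin C. The kidney injury item, however, begins "Patient experiences acute kidney injury as per clinical judgement by the investigator and/or according to the modified" guideline definition, so clinical judgement alone is enough to stop treatment.

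**The concern.** Two of the three creatinine-derived results are closed to the investigator once dosing starts, and the third is left open. Whatever the reason for footnotes 2 and 3, they cannot do their work while the same information arrives in another row. The report would also show the contrast that Section 1.2 ascribes to the drug: creatinine eGFR down, cystatin C eGFR level.

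An investigator who recognises that pattern could infer active treatment. One who does not could take it for renal decline and report an adverse event or stop treatment on clinical judgement. In either case the influence would tend to grow with dose. Early discontinuation is an intercurrent event. SAP Section 7.4.1 excludes UPCR measured after it and counts a missing week 12 value as non-response, so uneven stopping would reach the primary endpoint.

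**Working it through.** The plan gives no figure for the creatinine rise or for how visible it would be, so there is nothing to reproduce. The 73.4% in Protocol Section 7.5 is not an input here.

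**1. Does the open row return the withheld value?** Creatinine-only eGFR is, by its name, computed from serum creatinine. The formula is not printed in the protocol. I assume its other inputs are patient characteristics such as age and sex, which are effectively fixed over 12 weeks. Within a patient it is then a decreasing function of creatinine alone. Investigators also have the values up to visit 2 as a reference. A change in this eGFR therefore tells them the change in creatinine.

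**2. How many looks?** The safety laboratory row of Flow Chart A covers visits 3, 4, 5 and EoT after the first dose, which is four on-treatment results. The row appears to include FUP1 as well. Only the results from visits 3, 4 and 5 can prompt early stopping in a patient who would otherwise complete.

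**3. How visible might it be?** Let r be the proportional creatinine rise on drug and s the SD of the within-patient change in log creatinine. Both are assumed. With normal changes, the same s in both groups and no mean change on placebo, the chance that a random active patient shows a larger change than a random placebo patient is Φ[ln(1 + r) / (s√2)]. Example: r = 0.10, s = 0.08 gives Φ(0.0953 / 0.1131) = Φ(0.842) = 0.80.

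| Assumed rise | s = 0.08 | s = 0.12 | s = 0.16 |
|---|---|---|---|
| 5% | 0.67 | 0.61 | 0.59 |
| 10% | 0.80 | 0.71 | 0.66 |
| 20% | 0.95 | 0.86 | 0.79 |
| 30% | 0.99 | 0.94 | 0.88 |

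A value of 0.50 means the result carries no information. These figures use one result on creatinine alone; the contrast with cystatin C is not modelled.

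**4. What would one extra stop do?** Section 7.5 plans 15 patients per arm and assumes responder rates of 40%, 30% and 20% at 80, 40 and 20 mg. If the stopped patient would have responded, the arm loses 1/15 = 6.7 points. If responders and non-responders are equally likely to stop, the expected loss per stopped patient is:

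- 80 mg: 0.40/15 = 2.7 points
- 40 mg: 0.30/15 = 2.0 points
- 20 mg: 0.20/15 = 1.3 points

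These compare with the 25-point difference named as the goal. The documents give no basis for the number of extra stops.

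**The case against.** The strongest reply is that the governing text is partly hidden. The paragraph of Section 5.2.3 on which eGFR formula serves which purpose ends in redaction, and the laboratory manual is not available. Either could hold a masking rule. This stands: the finding is that no limit is visible for this row, not that none exists. If a rule does exist, the table still needs to agree with it.

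A reader might infer that the table is meant to protect the blind. The protocol does not say why creatinine is withheld. Avoiding misreading of a rise unrelated to filtration would explain footnotes 2 and 3 equally well. The inconsistency does not depend on the motive.

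A reader might also infer that sites will be unblinded and that one-sided stopping will bias the dose-placebo comparison. The documents do not support that:

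- The rise is not quantified.
- Both numeric renal stopping criteria use cystatin C, so only judgement is left as a route.
- Section 1.2 explains the rise as not reflecting kidney function. An investigator who recognises the pattern has less reason to stop for kidney injury, so the two harms partly work against each other.
- Extra stopping on active drug would lower its response rate. It would not by itself create a false positive.
- UPCR is a laboratory ratio, so its measurement is not directly exposed.
- The trial is exploratory, with no confirmatory testing.

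Finally, the local-laboratory fallback might be read as an equal leak. It is an exception that must be notified, so the unfootnoted row is the main route.

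**Conclusion.** The point holds as an inconsistency in the visible protocol with a real but unquantified risk to the double blind. Footnotes 2 and 3 withhold creatinine and the combined eGFR after visit 2, while the creatinine-only eGFR returns the same within-patient information next to the cystatin C eGFR.

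Uneven stopping or adverse event reporting across arms is possible through investigator judgement, but it is not demonstrated. Its size cannot be taken from the documents. The range in the table above, from little better than chance to near-complete separation, rests wholly on the assumed rise and SD. The conclusion also assumes that no redacted sentence or laboratory manual instruction already masks this row.

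**What to change.** 1. In Table 5.2.3: 1, apply the reporting limit of footnotes 2 and 3 (to the investigator only up to visit 2) to the creatinine-only eGFR row, and set the central laboratory report to match. Check first that this agrees with the redacted text of Section 5.2.3 and the laboratory manual.
2. For the local-laboratory fallback, remove no test. The documents do not say that local laboratories can run cystatin C, so dropping creatinine could leave the fallback panel without a renal marker. Instead, reconcile that paragraph with footnotes 2 to 4. Restrict the blinded trial team's view of local creatinine and creatinine-based eGFR recorded in the eCRF after visit 2. The site will still see results it obtains locally, so this narrows the secondary route without closing it.
3. When making these changes, confirm how post-visit-2 creatinine is handled in the central laboratory's periodic data transfer to the sponsor, which the visible text does not state.

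The cost is one footnote, one clarifying sentence, a report setting and an eCRF access setting. The downside is small: investigators no longer see a central value whose companion rows the plan already withholds. No eligibility criterion or numeric stopping criterion in the visible text uses creatinine-only eGFR, and cystatin C reporting is unchanged.
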